8.1.2. Serious Adverse Events (SAEs)

A serious adverse event (SAE) is an untoward medical occurrence or effect associated with the use of a study drug at any dose, regardless of whether it is considered to be related to the study drug, which results in one of the following:

- Death (ie, all deaths on treatment or within 6 weeks after last ataluren administration), including deaths due to progression of DBMD. Any death occurring later than 6 weeks following the last dose need not be reported as a serious adverse event unless it is a result of an event that started within the period covered by the on-study definition. The reported adverse event should be the event that caused the death. In addition, any adverse event resulting in death that occurs subsequent to the adverse event-reporting period and that the investigator assesses as possibly related to ataluren should also be reported as serious.
- Life-threatening adverse event. This is an event that, in the view of either the investigator or
 the sponsor, places the subject at immediate risk of death. It does not include an event that,
 had it occurred in a more severe form, hypothetically might have caused death.
- Inpatient hospitalization or prolongation of existing hospitalization (excluding
 hospitalizations for administration of ataluren, procedures required by the study protocol, or
 DBMD-related diagnostic procedures; other planned hospitalizations; or hospitalizations
 related only to progression of disease). Treatments in the emergency room for procedures
 such as hydration that do not require admitting the subject to the hospital and observational
 durations in the emergency room for less than 24 hours are not considered serious.
- Persistent or significant disability or incapacity or substantial disruption of the ability to conduct normal life functions, not related to DBMD.
- Any other medically important event that the investigator or the sponsor judges to be serious or which is defined as serious by the regulatory agency in the local country. Medical judgment should be exercised in deciding whether a reaction is serious in other situations. Important medical events that do not result in death, are not immediately life-threatening, and do not require hospitalization may be considered serious when, based on appropriate medical judgment, they may jeopardize the subject and may require medical or surgical intervention to prevent any of the outcomes listed above. Examples of such medical events include allergic bronchospasm requiring intensive treatment administration in an emergency room or at home, newly diagnosed malignancy, or blood dyscrasias, or convulsions that do not result in inpatient hospitalization, or the development of drug dependency or drug abuse.

An event need not be reported as a SAE if it exclusively represents a relapse or an expected change or progression of the baseline DBMD. This type of event need only to be reported as an adverse event.

Note that any SAEs occurring after the end of the patient's participation in the study should be reported to the sponsor if the investigator becomes aware of them.

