- A preexisting condition (eg, allergic rhinitis) must be noted on the appropriate electronic CRF (eCRF) for Visit 1, but should not be reported as an adverse event unless the condition worsens or episodes increase in frequency during the adverse event reporting period. Diagnostic and therapeutic non-invasive and invasive procedures, such as surgery, should not be reported as adverse events. However, the medical condition for which the procedure was performed should be reported if it meets the definition of an adverse event. For example, an acute appendicitis that begins during the adverse event reporting period should be reported as

the adverse event and the resulting appendectomy should be recorded in the source documents. If a surgical procedure was planned prior to entry into the study, and the surgery is not performed because of a worsening of a baseline condition, this should not be reported as an adverse event. Note that, as described in Section 8.1.2, any inpatient hospitalization occurring as the consequence of an adverse event during the study period should be reported as an SAE.

Each adverse event is to be classified as serious or nonserious by the investigator using medical and scientific judgment.

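### Protocol 8.1.2 counts deaths from DBMD progression as SAEs, then exempts progression events from SAE reporting without excepting fatal or life-threatening ones.

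*Protocol*

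**What the plan says.** **Deaths.** The first seriousness criterion in Protocol 8.1.2 covers "all deaths on treatment or within 6 weeks after last ataluren administration". It names deaths caused by the disease itself as falling under this rule: "including deaths due to progression of DBMD". Beyond that window, a death "following the last dose need not be reported as a serious adverse event unless it is a result of an event that started" during the time that counts as on-study. The section adds a separate provision for later fatal events that the investigator thinks possibly related to ataluren. It also says what to report: "The reported adverse event should be the event that caused the death".

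**Exemption.** The closing part of 8.1.2, referring to the disease as it stood at entry, reads: "An event need not be reported as a SAE if it exclusively represents a relapse or an expected change or progression". It adds a second sentence on how such an event is to be handled: "This type of event need only to be reported as an adverse event". Neither sentence mentions death or threat to life.

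**Hospitalizations.** Protocol 8.1.1, expressly referring the reader to 8.1.2, says that "any inpatient hospitalization occurring as the consequence of an adverse event during the study period should be reported as an SAE". The hospitalization criterion in 8.1.2 leaves out several kinds of admission, among them those "related only to progression of disease".

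**Use of the classification.** Protocol 8.9 and Table 8 make serious or non-serious status decide the reporting route. Serious events go to the sponsor's safety department within 24 hours; non-serious events follow the ordinary CRF procedure. Protocol 8.7 asks for follow-up within a further week for SAEs that are fatal or life-threatening. SAP 5.7.1 gives serious TEAEs their own tables, and tabulates and lists deaths separately.

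**The concern.** The safety profile is the primary endpoint (Protocol 3.3, SAP 3.3), and the count of serious events is a central part of it. Protocol 2.1 says that patients usually die of cardiac or pulmonary failure by 15 to 22 years of age, and treatment is planned for 240 weeks. Death or life-threatening deterioration attributed to the disease is therefore foreseeable, and it is the kind of event on which 8.1.2 gives two answers.

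The stake is consistency. Two sites with the same progression death could classify it differently, and each could cite the protocol. The event filed as non-serious would not be reported to the safety department within 24 hours and would not enter the serious-TEAE tables. The study has one arm and no concurrent control, so uneven classification across sites cannot be judged against a comparison group.

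**Working it through.** The plan gives no figure to reproduce. The sample size is not based on a hypothesis (Protocol 10.1, SAP 3.4), so the check is a comparison of texts.

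**Step 1. How each seriousness criterion in 8.1.2 treats DBMD progression, and what the closing exemption does to it.**

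| Criterion | Its own treatment of progression | Effect of the closing exemption |
|---|---|---|
| Death | Expressly included | Points the other way |
| Life-threatening | Silent | Removes it, if applied |
| Hospitalization | Progression-only admissions excluded | Agrees |
| Disability | DBMD-related disability excluded | Agrees |
| Other medically important event | Silent | Removes it, if applied |

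The conflict is direct for deaths. For life-threatening events, a criterion with no exclusion meets an exemption with no exception.

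**Step 2. Can the conflict be avoided by treating death as an outcome and progression as the event?** No. The Death criterion asks the site to report the event that caused the death. For a death due only to progression, that event is the progression, which is what the closing paragraph exempts.

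**Step 3. Is there a rule of precedence elsewhere?** Protocol 8.3, 8.7, 8.8 and 8.9, with Table 8, give none; 8.9 refers back to 8.1.2 for the classification. The SAP says that it overrides the protocol where the two conflict, but SAP 5.7.1 does not define a serious event, so it does not settle the matter.

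**Step 4. Hospitalizations.** Protocol 8.1.1 lists worsening of an existing illness among reportable adverse events, and the closing paragraph of 8.1.2 also calls progression an adverse event. On its wording alone, 8.1.1 therefore reaches a progression-only admission, which 8.1.2 leaves out. But 8.1.1 presents its sentence as a restatement of 8.1.2, and the two provisions inside 8.1.2 agree with each other. This is an incomplete cross-reference rather than a rival rule.

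**Step 5. Scale.** Inputs: planned maximum of about 96 boys (Protocol 1.2, SAP 3.4); number of boys affected not given.

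- Shift in the percentage with at least one SAE = (boys reclassified who have no other SAE) / 96 × 100.
- One boy: 1/96 × 100 = 1.04 points.
- If 1 to 10 boys were affected (an assumption for illustration): 1.0 to 10/96 × 100 = 10.4 points.

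This is the weight of each boy, not an estimate of impact.

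**The case against.** The strongest reply is that the exemption permits and does not forbid. It says that a progression event need not be an SAE, so a site that reports every progression death as serious complies with both sentences. The Death criterion is also the more specific rule, and reading the exemption over it would leave its reference to progression deaths without effect. This stands in part. It disposes of the stronger claim, which a reader might infer, that a site cannot obey all the sentences at once. It does not remove the defect: the protocol never says that the specific rule prevails, and a permissive sentence still gives cover to a site that does not report.

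A reader might put the hospitalization mismatch on the same footing as the deaths. The documents do not support that, because 8.1.1 points to 8.1.2 and most readers would carry its exclusions across.

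A reader might also infer that a harmful effect of ataluren on cardiac or respiratory decline would be filed as non-serious. That goes too far. The exemption covers only events that are purely progression, so one with a suspected drug contribution falls outside it. Exempted events remain adverse events and can appear in the Grade 3 or higher TEAE tables. Deaths are tabulated and listed separately. Protocol 9 requires evaluation of cardiac worsening in consultation with the sponsor's medical monitor, SAP 5.8.5 and 5.8.7 summarize spirometry and ejection fraction by visit, and a DMC reviews accumulating data. What remains exposed is the serious label and the reporting time. Life-threatening progression events have less backup than deaths, since SAP 5.7.1 plans no separate listing for them.

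Finally, the 9 to 21 year range in SAP 8.2 might be taken to show that participants reach the ages of fatal failure. It is a matching filter for the natural-history comparison on certain spirometry endpoints, not a stated enrolment range, so nothing here rests on it.

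**Conclusion.** The concern holds for deaths, and as an unresolved question for life-threatening events. Section 8.1.2 contains a rule that includes progression deaths among SAEs and an exemption that, as worded, allows them to be left out. Nothing in the protocol or SAP ranks the two. The consequence is possible inconsistency in SAE classification, 24-hour reporting and the serious-TEAE tables. It is not loss of the events, and no hypothesis test or error rate is affected.

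The size is about 1 percentage point in the proportion with at least one SAE for each affected boy. This assumes a denominator of 96 and that the boy has no other SAE. The documents do not say how many boys are affected, or whether any site has used the exemption for a death.

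The hospitalization wording is a lesser drafting gap. A reader might conclude that all admissions attributed to progression should go on SAE forms. The documents do not support that as a correction: leaving out progression-only admissions is an explicit sponsor choice in 8.1.2, and requiring them would replace that choice rather than reconcile the text.

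**What to change.** 1. In the closing paragraph of Protocol 8.1.2, state that the exemption does not apply to deaths covered by the Death criterion. This follows the section's own explicit rule.
2. Have the sponsor state in the same place whether the exemption applies to life-threatening events. The documents do not settle this.
3. In Protocol 8.1.1, add to the hospitalization sentence: *subject to the exclusions in Section 8.1.2*.
4. For data already collected, identify deaths whose reported event is disease progression and check that those meeting the Death criterion are classified as serious before the SAP 5.7.1 serious-TEAE tables are run. The search should use fatal outcome as well as the event term, because SAP 5.8.2 also uses disease-progression adverse events to mark loss of ambulation.

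SAP 5.2 records the sponsor's decision to discontinue the study, so step 4 is likely to matter most for the final report. The cost is two short wording changes, a sponsor statement, notice to sites still active, and one data query. The downside is a few more SAE forms and slightly higher SAE counts.

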8.1.3. Unexpected Adverse Events

Unexpected adverse events are defined as those events that were not previously reported with ataluren as referenced in the most current investigator brochure, or that are symptomatically and pathophysiologically related to a known toxicity but differ because of greater severity or specificity. For example, under this definition, hepatic necrosis would be unexpected (by virtue of greater severity) if the investigator brochure only referred to elevated hepatic enzymes or hepatitis. Similarly, cerebral thromboembolism and cerebral vasculitis would be unexpected (by virtue of greater specificity) if the investigator brochure only listed cerebral vascular accidents. "Unexpected," as used in this definition, also refers to an adverse event that is mentioned in the most current investigator brochure as occurring with the class of drugs or as anticipated from the pharmacological properties of the study drug, but is not specifically mentioned as occurring with ataluren.

For the purposes of considering expectedness, Section 9 of the ataluren investigator brochure provides a summary of the safety profile of ataluren based on available clinical information (also referred to as the reference safety information).

8.2. Eliciting Adverse Event Information

The investigator is to report all directly observed adverse events and all adverse events spontaneously reported by the study subject or parent/guardian in case of a child. In addition, each study subject will be questioned about adverse events at each scheduled clinic visit after ataluren administration or during any telephone contact with the subject or parent/guardian in case of a child. The type of question asked should be open-ended, eg, "How has your child been feeling?" or a similar type of query.

8.3. Adverse Event Recording

All adverse events (both serious and nonserious) that occur in patients during the adverse event reporting period must be recorded, whether or not the event is considered drug related. In addition, any known untoward event that occurs subsequent to the adverse event reporting period that the investigator assesses as possibly related to the investigational drug/product should also be recorded as an adverse event.

All adverse events are to be recorded in the source documents and on the CRF using concise medical terminology; whenever possible terms contained in Medical Dictionary for Regulatory Activities (MedDRA) should be employed. In addition, the following information should be recorded:

Indication of whether the event is serious or nonserious (see Section 8.1.2)

- Relationship to ataluren (see Section 8.4)
- Severity of the event (see Section 8.5)
- Onset date
- Resolution date, or date of death
- Action taken
- Outcome of the event

Classification of the event as serious or nonserious determines the reporting procedures to be followed.

8.4. Describing Adverse Event Relationship to Study Drug

Based on the considerations outlined in Table 6 below, the investigator should provide an assessment of the relationship of the adverse event to the study drug, ie, whether there is a reasonable possibility that the study drug caused the adverse event.

Table 6. Relationship of Study Drug to Adverse Event

	Table 6. Relationship of Study Drug to Adverse Event				
Relationship	Description				
Probable	A clinical event in which a relationship to the study drug seems probable because of such factors as consistency with known effects of the drug; a clear temporal association with the use of the drug; improvement upon withdrawal of the drug; recurrence upon rechallenge with the drug; lack of alternative explanations for the event.				
Possible	A clinical event occurring coincident with administration of the study drug and which may or may not be explained by concurrent disease or other drugs or chemicals. Information on drug withdrawal or rechallenge may be lacking.				
Unlikely	A clinical event with a temporal relationship to the study drug exposure that does not preclude causality but for which there is a clear alternate cause that is more likely to have caused the adverse event than study drug. Such alternatives include a concomitantly administered drug, the subject's disease state, other medical conditions, or environmental factors.				
Unrelated	A clinical event, for which a relationship to the study drug seems improbable because of factors such as inconsistency with known effects of the study drug, lack of a temporal association with study drug administration, lack of association of the event with study drug withdrawal or rechallenge, and/or presence of alternative explanations for the event. Alternative explanations might include a known relationship of the adverse event to a concomitant drug, medical history of a similar event, the subject's disease state, other medical conditions, or environmental factors.				

8.5. Grading of Severity of Adverse Events

The severity of adverse events will be graded using the CTCAE, Version 3.0 (refer to Study Manual or to http://ctep.cancer.gov/forms/CTCAEv3.pdf). For each episode, the highest severity grade attained should be reported.

If a CTCAE criterion does not exist, the investigator should use the grade or adjectives: Grade 1 (mild), Grade 2 (moderate), Grade 3 (severe), Grade 4 (life-threatening), or Grade 5 (fatal) to describe the maximum intensity of the adverse event. For purposes of consistency with the CTCAE, these intensity grades are defined in Table 7.

Table 7. Grading of Adverse Event Seventy				
Grade	Adjective	Description		
Grade 1	Mild	Sign or symptom is present, but it is easily tolerated, is not expected to have a clinically significant effect on the subject's overall health and well being, does not interfere with the subject's usual function, and is not likely to require medical attention		
Grade 2	Moderate	Sign or symptom causes interference with usual activity or affects clinical status, and may require medical intervention		
Grade 3		Sign or symptom is incapacitating or significantly affects clinical status and likely requires medical intervention and/or close follow-up		
Grade 4	Life-threatening	Sign or symptom results in a potential threat to life		
Grade 5	Fatal	Sign or symptom results in death		

Table 7. Grading of Adverse Event Severity

Note the distinction between the seriousness and the severity of an adverse event. Severe is a measure of intensity, thus, a severe reaction is not necessarily a serious reaction. For example, a headache may be severe in intensity, but would not be classified as serious unless it met one of the criteria for serious events listed in Section 8.1.2 above.

8.6. Pregnancy of Female Partners

PTC Therapeutics should be notified in the event that a female partner of a subject becomes pregnant at any time after the subject's first dose of ataluren. Any such pregnancy occurring on-study or within 60 days of the last administration of ataluren must be reported on a Pregnancy Notification Form (see Study Manual for details). This must be done whether or not an adverse event has occurred and within 24 hours of awareness of the pregnancy. The information submitted should include the anticipated date of birth or pregnancy termination.

Written consent is required prior to collecting and reporting any information on a female partner of a subject.

If possible, the investigator should follow the pregnant female partner of the subject until completion of the pregnancy and notify the PTC Therapeutics medical monitor of the outcome within 5 days or as specified below. The investigator will provide this information as a follow up to the initial Pregnancy Notification Form via the Pregnancy Outcome Form (see Study Manual for details).

If the outcome of the pregnancy meets the criteria for immediate classification as a serious adverse event (ie, spontaneous abortion, stillbirth, neonatal death, or congenital anomaly [including that in an aborted fetus]), the investigator should follow the procedures for reporting serious adverse events, ie, report the event to the PTC Therapeutics Safety Department and follow up by submission of appropriate adverse event CRFs (see Section 8.9).

8.7. Follow-Up of Unresolved Adverse Events

All adverse events should be followed up by the investigator until they are resolved, or the investigator assesses them as chronic or stable. Follow-up of any SAE that is fatal or life-threatening should be provided within one additional calendar week. The investigator should consider protocol guidelines and use his/her discretion in ordering additional tests as necessary to monitor the resolution of such events. In the event of additional investigations, the PTC Therapeutics Safety Department should be informed via e-mail or fax. A subject withdrawn from the study because of an adverse event must be followed by the investigator until clinical

recovery is complete and laboratory results have returned to normal, or until progression has been stabilized. Follow-up may need to continue after the subject has discontinued from the study, and additional investigations may be requested by the medical monitoring team.

8.8. Adverse Event Reporting Period

The first day of adverse event reporting will coincide with the day the first dose of ataluren is administered. The adverse event reporting period for this study ends with the 6-week (± 7 days) Post-Treatment Visit, except as described in Section 8.7 above. In addition, SAEs occurring in a subject after the study period should be reported to the sponsor if the investigator becomes aware of them.

8.9. Investigator Site Adverse Event Reporting Requirements

Classification of an event as serious or nonserious (see Section 8.1.2) determines the reporting procedures to be followed. Investigator site reporting requirements for adverse events are summarized in Table 8 below.

Table 8. Investigator Site Reporting Requirements for Adverse Events

Classification	Reporting Time	Reporting Action	
Serious	Within 24 hours	Telephone call, fax, or e-mail to the PTC Therapeutics Safety Department	
	Within 24 hours	Fax report or document scan on designated SAE report form to the PTC Therapeutics Safety Department and to site IRB/IEC, as per local IRB/IEC requirements	
	Within 5 calendar days	Photocopies or document scan of relevant CRFs (eg, adverse event form, medical history form, concomitant drug/therapy form) and source documents ^a (eg, progress notes, nurses' notes, laboratory and diagnostic test results, discharge summaries) to the PTC Therapeutics Safety Department	
	Per CRF submission procedure	Record and submit information on appropriate CRFs	
Nonserious	Per CRF submission procedure	Record and submit information on appropriate CRFs	

Subject name, address, and other personal identifiers should be obscured.

Abbreviations: CRF = case report form, IRB/IEC = Institutional Review Board/Independent Ethics Committee, SAE = Serious Adverse Event

For SAEs, in addition to completing the adverse event portion of the CRF, the SAE report form must also be completed. The SAE report form should be signed by the investigator; however, if the investigator is unable to sign at the time of the event or within 24 hours, the form should be signed by the clinical staff member reporting the SAE (eg, the study coordinator). The SAE report form must be faxed or emailed to the PTC Therapeutics Safety Department and to the site IRB/IEC (if required by local regulations) within 24 hours. Follow up information to the SAE should be clearly documented as "follow up" in the SAE report form and must also be faxed or emailed to the same party. All follow up SAE report forms for the event must be signed by the investigator. Any source documents (eg, progress notes, nurses' notes, laboratory and diagnostic test results, discharge summaries) provided to the sponsor should be redacted so that the patient's name, address, and other personal identity information are obscured. Only the patient's study number and initials are to be provided. The information in the adverse event portion of the CRF and the SAE report form(s) must match or be reconciled. Where the same data are collected, the

forms must be completed in a consistent manner. For example, the same adverse event term should be used on both forms.

In the rare event that the investigator does not become aware of the occurrence of an SAE immediately (for example, if a subject initially seeks treatment elsewhere), the investigator is to report the event within 24 hours after learning of it and to document his/her first awareness of the adverse event.

The PTC Therapeutics Safety Department contact information for reporting serious adverse events is provided below. This information is also provided in the Study Manual and in the SAE report form.

